The standardization of the data to common terms and application of the Evidian knowledge base are key process steps in gathering data from multiple heterogeneous EHR systems and databases from many locations into a single, homogenous OPERA database for conducting research and commercial analyses. The patient health data gathered, classified and aggregated includes complete medical history & social history, visit dates, vital signs, lab orders and results, medications, problems & diagnoses, and procedures.

Evidian has developed rigorous data management processes that include both automated and manual quality checks. Data quality methods include common techniques such as:

- Detection and reporting of outliers that lead to correction, acceptance, or exclusion of observations; these can include a medical review.
- Detection of potentially missing data (e.g., a patient taking ART medications with no history of HIV infection to determine whether the use was prophylactic or treatment for infection diagnosed elsewhere).
- Data completion using multiple observations and sources (e.g., using diagnoses codes, free text, past medical history, etc. to determine if patient is naive to HIV therapy).
- Detection of observations that are known to be (or likely to be) mutually exclusive for a patient (e.g., record of medications that are typically not administered concurrently).

5. Study Population

Individuals presenting for care at AHF Midtown Manhattan Healthcare Center and followed through their electronic health records in the OPERA Observational Database.

INCLUSION CRITERIA

Patients who were:

1. Cared for at AHF Midtown Manhattan Healthcare Center and followed in the OPERA observational database
2. Active in care in the last 24 months
3. Fully vaccinated against SARS-CoV-2 virus, implemented as 21 days after the second Pfizer or Moderna injections, 21 days after the one J&J injection
4. Received a Roche SARS-CoV-2 Semi-Quant Spike Ig AB test after full vaccination as usual clinical care
5. ≥ 18 years of age at vaccination

EXCLUSION CRITERIA

Patients who were:

1. Unvaccinated or partially vaccinated against SARS-CoV-2 virus
2. Never tested with a SARS-CoV-2 Semi-Quant Total AB test after full vaccination

6. Study Design

OVERVIEW OF STUDY DESIGN

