The design for this study is an observational cohort study utilizing prospectively collected electronic medical record (EMR) data from usual clinical care at AHF Midtown Manhattan Healthcare Center, obtained from the OPERA® Observational Database.

The study population will consist of adults vaccinated against SARS-CoV-2 virus receiving the Roche SARS-CoV-2 Semi-Quant Spike Ig AB test as part of their usual clinical care. These individuals will be followed from vaccination until study end.

EXPOSURES OF INTEREST

Initial vaccination with Pfizer, Moderna, and J&J COVID vaccines, booster vaccination with Pfizer, Moderna, and J&J vaccines, and concordant boosting versus discordant boosting

SUBGROUPS OF INTEREST

HIV-positive versus HIV-negative patients, individuals with at least 2 measurements of antibody levels, and boosted individuals are the subgroups of interest.

STUDY ENDPOINTS

Endpoints for both the primary and secondary objectives are non-responders and low responders and rates of decline of SARS-CoV-2 antibodies

- Non-response will be defined as: 0 to <50 U/mL
- Low response will be defined as: ≥ 51 to ≤ 250 U/mL
- Adequate response will be defined as: >251 U/mL

Roche's Elecsys semi-quantitative spike Ab Ig assay is a commercially available assay that can potentially be utilized to help guide the need for an additional vaccination dose based upon the levels of antibodies that have been previously clinically correlated with neutralizing antibodies. As part of routine care, Ab Ig assays were performed for some patients at the AHF Midtown Manhattan Healthcare Center and results were recorded in their EHR.

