To normalize across different neutralization assays utilized in phase 3 studies of various COVID-19 vaccines, Khoury, et al., estimated that a 50% protective neutralization level equivalent to 20% of the mean titer in the convalescent subjects equates to a measured in vitro neutralization titer of between 1:10 and 1:30 was approximated at 54 international units IU/ml (95% CI 30–96 IU/ml) against wild-type CoV-19 infection.^{xx} During the period of COVID-19 infection where the Delta virus predominated, a quantitative spike Ab's >250 IU/mL was deemed adequate, based on studies that show that an antibody titer of 4-6x wild-type SARS-CoV-2 were required to effectively neutralize Delta viral strains.^{xxi,xxii, xxiii} We thus utilized a threshold level of >250 (5x wild-type ab levels) IU/mL as an adequate vaccine response against circulating Delta virus post last vaccination recommended in a series, a level of <50 IU/mL as a non-responsive post vaccination titer (inadequate for even wild-type Co-V-2 infection), and levels between (50-250 IU/mL) as a low vaccine response. Non and low-responders who had Co-V-2 Spike Ig levels that were inadequate based on the correlation of Spike Ig levels and neutralizing ab correlations relative to the predominant circulating viral strains were offered optional booster vaccinations with subsequent antibody response measurement post vaccination as standard of care. These recommendations are the current one's implemented during the Delta Co-V-2 19 outbreak by the Ministry of Solidarity and Health of France and the COVID Guidelines group in Geneva, where 260 IU/mL and 300 IU/mL, respectively, are considered gray zones of antibody protection against the Delta virus and where booster vaccinations are recommended for consideration.^{xxiv, xxv}

STUDY COVARIATES

Covariates of interest include: age, sex, race, ethnicity, HIV status, region, payer, immunosuppressive conditions, CD4 cell count, comorbid conditions, BMI. This information will be obtained from each patient's electronic health records.

7. Statistical Analysis

ANALYSIS OF DEMOGRAPHICS/BASELINE CHARACTERISTICS

Demographic and clinical characteristics will be summarized in the overall population using medians with interquartile ranges (IQR) for continuous variables and frequencies with proportions for categorical variables.

ANALYSIS OF PRIMARY OBJECTIVES

Objective #1: COVID-19 vaccine non-response and low response as measured by antibody test by HIV status

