Records will be examined retrospectively to determine which patients, both HIV-positive and negative, were non-responders, or who developed low or adequate quantitative Ig spike antibodies using the Roche Elecsys semi-quantitative spike Ab Ig assay during usual clinical care.

Demographic and clinical characteristics will be summarized by vaccine response level using medians with interquartile ranges (IQR) for continuous variables and frequencies with proportions for categorical variables. Statistical comparisons between vaccine response level will be performed using Pearson's chi-square or Fisher exact tests for categorical variables and Wilcoxon rank-sum test for continuous variables, using an adequate response as the comparator.

Incidence rates and 95% confidence intervals of COVID vaccine adequate response, non-response and low response to COVID vaccines will be estimated using univariate Poisson regression. Incidence rates will be obtained both overall and by vaccine type. The incidence rate is defined as the number of events during follow-up divided by person-time at risk of the event. Estimating incidence rates with Poisson regression allows the use of all person-time time at risk of the outcome, even with differential lengths of follow-up between groups.

Objective #2: Rate of decline in antibody levels over time by HIV status, vaccine type, and baseline CD4 count after initial vaccination

Rates and 95% confidence intervals of antibody levels decay will be estimated among individuals with at least two antibody measurements. Univariate linear regression, will be employed, using the continuous antibody level as the dependent variable, and timing of tests as

the dependent variable. Robust variance estimator will be used to account for repeated measures. Rates of decay will be produced overall, and stratified by HIV status, vaccine type and baseline CD4 cell count.

ANALYSIS OF SECONDARY OBJECTIVES

Objective #3: COVID-19 boosters given

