In the sub-population of Individuals who received a COVID vaccine booster, the following characteristics will be described using medians with interquartile ranges (IQR) for continuous variables and frequencies with proportions for categorical variables: initial and booster vaccine types, concordant vs. discordant boosters, duration between initial vaccine completion and booster dose, antibody response after the booster, and side effects recorded. Post vaccination responses will be determined no earlier than 2 weeks post vaccination.

Objective #4: Rate of decline in antibody levels over time by HIV status, booster type, and baseline CD4 count after booster vaccination

Rates and 95% confidence intervals for changes in antibody levels will be estimated using linear regression, among individuals with at least two antibody measurements, including one after the booster dose. Univariate linear regression, will be employed, using the continuous antibody level as the dependent variable, and timing of tests as the dependent variable. Robust variance estimator will be used to account for repeated measures. Rates of decay will be produced overall, and stratified by HIV status, booster type and baseline CD4 cell count.

Objective #5: Recording breakthrough infections after vaccinations and assessing antibody levels pre-breakthrough infection

Among all individuals with full vaccination and antibody testing, the EHR will be searched for documentation of COVID infection after vaccinations. If breakthrough infections are observed, antibody levels prior to infection will be described. Note: COVID infections may not be recorded in the EHR if diagnosed outside of the clinic.

SENSITIVITY ANALYSES

NA

SUBGROUP ANALYSES

Patients provided COVID boosters will be evaluated by the types and combinations of vaccines they received. Further, patients given sequential antibody tests will be evaluated by vaccine type for response over time.

8. Study Conduct

REGULATORY AND ETHICAL CONSIDERATIONS

OPERA® complies with all HIPAA and HITECH requirements and has received annual institutional review board (IRB) approval by Advarra IRB, including a waiver of informed consent and authorization for use of protected health information

INFORMED CONSENT

Informed consent has been waived for this non-interventional, observational research and authorization for use of the protected health information has been approved by Advarra IRB.

DATA PRIVACY & PERSONALLY IDENTIFIABLE INFORMATION (PII)

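### No rule separates infection-driven from vaccine-driven spike titres, so apparent vaccine response is inflated and the raw-scale decay slopes are biased in a direction that cannot be fixed in advance

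*Combined protocol and SAP*

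**What the plan says.** Section 5 has two exclusion criteria: "Unvaccinated or partially vaccinated against SARS-CoV-2 virus" and "Never tested with a SARS-CoV-2 Semi-Quant Total AB test after full vaccination". No inclusion criterion mentions infection. Section 6, Study Covariates, reads: "Covariates of interest include: age, sex, race, ethnicity, HIV status, region, payer, immunosuppressive conditions, CD4 cell count, comorbid conditions, BMI". On follow-up, section 6 says: "These individuals will be followed from vaccination until study end".

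Response is classed by titre alone. Section 6, Study Endpoints, states: "We thus utilized a threshold level of >250 (5x wild-type ab levels) IU/mL as an adequate vaccine response".

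In section 7, Objective 1 rates of adequate, non- and "low response to COVID vaccines will be estimated using univariate Poisson regression". For Objective 2, "Rates and 95% confidence intervals of antibody levels decay will be estimated among individuals with at least two antibody measurements", by univariate linear regression of the continuous titre on test timing. Objective 4 uses the same model after boosters. The decay strata are HIV status, vaccine or booster type, and baseline CD4 count. Sensitivity Analyses is marked NA, and Subgroup Analyses concerns vaccine types and combinations.

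Infection enters only in Objective 5, where "the EHR will be searched for documentation of COVID infection after vaccinations" and any titres before infection are described. The plan adds that infections diagnosed outside the clinic may be missing.

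**The concern.** A spike titre does not show whether vaccination or infection produced it. The plan's own protection threshold is scaled to titres in convalescent subjects. A previously infected patient with a poor vaccine response can therefore be classed as an adequate responder. If infection history differs by HIV status or vaccine type, two groups with the same vaccine response will appear to differ.

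The decay analyses are exposed in a second way. An infection between two tests raises the later titre and masks waning. An infection before vaccination raises the starting titre, and so the absolute amount lost per day.

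The first problem affects Objective 1 and the second Objective 2, both primary. The synopsis says the titres are meant to help guide booster timing, so an error in apparent response or in decay bears directly on the study's purpose.

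**Working it through.** **What the plan controls.** Infection is not excluded (section 5), not a listed covariate and not an end of follow-up (section 6), not a stratum, and not covered by a sensitivity analysis (section 7). Reading the comorbidity item to include past COVID-19 would not help, because the response-rate and decay models are univariate and adjust for nothing. Objective 5 does not look before vaccination, and its findings are not carried into Objectives 1-4.

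**Size.** The plan states no infection rate, titre distribution, fold-rise or half-life, so there is no planned figure to reproduce. All inputs below are assumptions.

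*Response (Objective 1).* Assume an infection-naive geometric mean of 800, SD 0.5 log10, and a 5-fold higher titre after prior infection (geometric mean 4,000).
- Naive share at or below 250: Φ[(log10 250 − log10 800)/0.5] = Φ(−1.01) = 15.6%.
- Previously infected: Φ[(log10 250 − log10 4,000)/0.5] = Φ(−2.41) = 0.8%.
- 10% infected: 0.9 × 15.6% + 0.1 × 0.8% = 14.1%.
- 30% infected: 0.7 × 15.6% + 0.3 × 0.8% = 11.2%.
- A 30%-infected group against a 10%-infected group: 11.2/14.1 = 0.79, with identical vaccine response. With equal infection history the ratio is 1.

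*Infection between tests (Objectives 2 and 4).* Assume a 70-day half-life, tests 120 days apart and a 10-fold rise. Set the naive mean first titre to 1.
- Fraction remaining: 0.5^(120/70) = 0.305. Uninfected change: −0.695 raw, −0.516 log10.
- Infected change: 10 × 0.305 − 1 = +2.05 raw, −0.516 + 1 = +0.484 log10.
- 5% infected: raw 0.95(−0.695) + 0.05(2.05) = −0.558, about 20% weaker; log10 −0.466, about 10% weaker.
- 10% infected: raw −0.421, about 39% weaker; log10 −0.416, about 19% weaker.
- With a 3-fold rise in 5%: infected change 3 × 0.305 − 1 = −0.086; mean 0.95(−0.695) + 0.05(−0.086) = −0.665, about 4% weaker.
- One patient's decline becomes a rise only if the fold-rise exceeds 1/0.305 = 3.3.

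*Infection before vaccination, same decay model.* A 5-fold starting titre loses 5 × 0.695 = 3.475 over the interval.
- 10% previously infected: 0.9(−0.695) + 0.1(−3.475) = −0.973, or 40% steeper. The log change stays at −0.516 if the proportional decay rate is the same.

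*Both together, assumed independent, raw scale, against an infection-free cohort.* The between-test factors are 0.558/0.695 = 0.803 at 5% and 0.421/0.695 = 0.606 at 10%. The prior-infection factors are 1.4 at 10% and 1 + 0.3 × 4 = 2.2 at 30%.

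| Previously infected | Infected between tests | Factor | Raw slope |
|---|---|---|---|
| 10% | 5% | 1.4 × 0.803 = 1.12 | 12% steeper |
| 30% | 10% | 2.2 × 0.606 = 1.33 | 33% steeper |
| 10% | 10% | 1.4 × 0.606 = 0.85 | 15% flatter |

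**Check under different assumptions.** A simulation fitted a pooled raw-titre slope to two tests per person. It assumed a geometric mean of 600 at day 0, natural-log SD 1.2, a 90-day half-life, a first test at day 21-120 and a second 30-120 days later.
- No infection: −4.1 U/mL/day.
- 10-fold rise between tests in 2%, 5% or 10%: −3.7, −3.2 and −2.2.
- 10% infected between tests, 3- to 30-fold rise: −3.7 to +2.1.
- 5-fold higher titre from prior infection in 10% or 30%: −5.7 and −9.1, with the log slope unchanged at −0.0077 per day.

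The directions agree with the hand calculation. The sizes depend heavily on the inputs.

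**The case against.** A reader might infer that infection at any time makes waning look too slow. The calculations do not support that: only infection between tests flattens the slope, and pre-vaccination infection works the other way on the planned raw scale. A reader might also take 39% or 0.79 as the expected bias. Nothing in the documents supports either figure. The 0.79 needs a 30%-against-10% contrast in infection history, and no such contrast by HIV status or vaccine type is documented. Nor does the plan say that tests after a breakthrough infection are kept. It is silent, and they enter because nothing removes them.

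The remedy has limits too. Adding infection to the covariate list changes nothing in univariate models. Infections diagnosed elsewhere may be missing, and capture could differ by HIV status: section 4 gives median clinic follow-up of 7.3 years in HIV-positive and 4.9 years in HIV-negative patients. Stratifying on documented infection could therefore bring differential misclassification into that comparison. Censoring can leave patients with fewer than two tests. It may also be informative, since the Background links waning antibody to infection risk.

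All of this stands. It limits what can be said about direction and size and shapes the remedy, but it does not supply the missing rule.

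**Conclusion.** The omission is confirmed from the text, and the sponsor should correct it. As written, titres due to infection count as vaccine response and enter the decay slopes. Inflation of apparent response is the predictable direction for Objective 1; bias between groups follows only if infection history differs between them. For Objectives 2 and 4 the net raw-scale bias has indeterminate sign. On a log scale only the flattening from infection between tests remains, provided the proportional decay rate is the same in previously infected patients. The size cannot be derived from the documents. The figures above show that modest infection shares could matter, and that smaller fold-rises matter much less.

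**What to change.** - Extend the Objective 5 record search to any time before each antibody test, using the diagnoses, laboratory results and medical history that section 4 says the database holds.
- Report Objectives 1-4 stratified by documented prior infection. Listing it as a covariate is not enough.
- In Objectives 2 and 4, censor titres at the first documented post-vaccination infection, and report the uncensored analysis alongside.
- Replace NA under Sensitivity Analyses with a repeat of Objectives 1, 2 and 4 in patients with no documented infection.
- State that capture is incomplete and may differ by HIV status, that censoring may be informative, and how many patients fall below two measurements.

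The cost is one wider query, revised analysis wording and some lost post-infection tests. No new visits or samples are needed. Residual bias from unrecorded infections remains.

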The study population will include adults who were fully vaccinated against SARS-CoV-2 virus (i.e., two doses of Pfizer or Moderna vaccines or one dose of the J&J vaccine), and have received a Roche SARS-CoV-2 Semi-Quant Spike Ig Ab test at least 3 weeks after full vaccination as part of their usual clinical care at AHF Midtown Manhattan Healthcare Center.

Incidence rates of COVID vaccine response levels (i.e., adequate, low, non-response) will be estimated using univariate Poisson regression, overall and by vaccine type. Among individuals with at least two antibody measurements, rates of antibody levels decay will be estimated using univariate linear regression, overall and stratified by HIV status, vaccine type and baseline CD4 cell count. In the sub-population of individuals who received a COVID vaccine booster, vaccination and antibody response will be characterized at least 3 weeks after the booster is received. Univariate linear regression will be used to estimate rates of antibody levels decay, among individuals with at least two antibody measurements, including one after the booster dose. Rates of response decay will be produced overall, and stratified by HIV status, booster type and baseline CD4 cell count.

2. Introduction

BACKGROUND

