Limited real-world data are available on the antibody response after COVID-19 vaccination comparing HIV-negative and HIV-positive individuals. There are also limited information that would allow the potential usage of quantitative antibody testing to determine those at greatest risk for infection while could help in guiding the timing of additional vaccinations. There are also limited information on the antibody response of vaccine boosting in individuals, especially those with altered immune response that might lead to no response or low response to the primary vaccination series. At the moment, clinicians must rely on clinical judgement when advising their patients on the utility of vaccine boosting, as well as their level of protection from COVID vaccination. Additional information would be helpful in informing decisions on third doses in different populations such as HIV positive people, whose responses to COVID-19 vaccine and immune status would help define the timing and need for an additional vaccination based on current recommendations. Real-world evidence is needed to better inform such decisions.

3. Research Objectives

PRIMARY OBJECTIVE(S)

Objective #1: Describe COVID-19 vaccine response including frequency of non-response, low response, and adequate response as measured by antibody test by HIV status (e.g., rates, and relationship to demographic and clinical characteristics, as well as vaccine types)

Objective #2: Describe rate of decline in antibody levels over time by HIV status, vaccine type, and baseline CD4 count after initial vaccination as well as other parameters.

SECONDARY OBJECTIVE(S)

Objective #3: Describe response to COVID-19 boosters given (vaccine types, concordant vs. discordant boosters, duration from initial vaccine completion, antibody response, and side effects)

Objective #4: Describe rate of decline in antibody levels over time by HIV status, baseline CD4 count, by vaccine given, and after booster vaccination

Objective #5: Recording breakthrough infections after vaccinations and assessing antibody levels pre-breakthrough infection

4. Data Source

AHF MIDTOWN MANHATTAN HEALTHCARE CENTER

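### Objective 1 asks how often each response level occurs, but its only planned interval estimate is a rate per person-time, which is not that frequency and depends on an unstated rule for time at risk

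*Combined protocol and SAP*

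**What the plan says.** Section 3 sets the target of the first primary objective: "Describe COVID-19 vaccine response including frequency of non-response, low response, and adequate response as measured by antibody test by HIV status". A parenthesis after it gives *rates* as one example of what may be described. The Section 7 heading for this objective repeats the split by HIV status.

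The estimator is named twice. The synopsis says "Incidence rates of COVID vaccine response levels (i.e., adequate, low, non-response) will be estimated using univariate Poisson regression". Section 7 (Objective #1) repeats this with 95% confidence intervals and defines the measure: "The incidence rate is defined as the number of events during follow-up divided by person-time at risk of the event". It then fixes the strata: "Incidence rates will be obtained both overall and by vaccine type". The reason given for Poisson regression is that it uses all time at risk when groups are followed for different lengths of time.

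The response levels are titer bands (Section 6, Study Endpoints). They are read from a test that every included patient must have had. Section 5 requires patients who "Received a Roche SARS-CoV-2 Semi-Quant Spike Ig AB test after full vaccination as usual clinical care". On follow-up, Section 6 says only "These individuals will be followed from vaccination until study end". No study-end date is given. For Objective 1 there is no rule on whether time stops at the test or at a booster, or on which test counts when there are several.

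HIV status appears among the covariates ("Covariates of interest include: age, sex, race, ethnicity, HIV status, region, payer"). Section 7 also plans a table of demographic and clinical characteristics by response level. Sensitivity analyses are marked as not applicable.

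**The concern.** The frequency of a response level is a proportion: patients at that level divided by patients tested. The planned quantity divides the same count by accumulated time. For a patient classified once after the primary series, later follow-up cannot add to the numerator. It can only enlarge the denominator.

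The main interval estimate for a primary objective would therefore answer a different question from the one posed, and it would not be split by HIV status, which the objective names. The rates will also be set side by side by vaccine type. If mean person-time differs between vaccine groups, part of any contrast will reflect calendar timing and not response.

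**Working it through.** The documents give no response counts, test timing or numerical rate, so there is no figure of the plan's own to reproduce. **All inputs below are assumed**, with one classification per patient. Write p for the proportion at a level, T for mean years from vaccination to study end, and m for years from vaccination to the event or test.

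**One cohort, 160 of 200 adequate (p = 0.80), study end at 6 or 9 months**

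- *(a) Everyone contributes time from vaccination to study end.* Rate = p/T.
  - 6 months: 160/(200 × 6/12) = 160/100 = 1.60 per person-year. The 95% CI is 1.60 × exp(±1.96/√160) = 1.37 to 1.87.
  - 9 months: 160/(200 × 9/12) = 160/150 = 1.07 (0.91 to 1.25).
  - This is a fall of 33% with no new patient or test.
- *(b) Time stops at the event, here at month 2; the others run to study end.* Rate = p/(p·m + (1 − p)·T).
  - 6 months: 160/(160 × 2/12 + 40 × 6/12) = 160/46.67 = 3.43.
  - 9 months: 160/(160 × 2/12 + 40 × 9/12) = 160/56.67 = 2.82.
  - This is a fall of 18%.
- *(c) All time stops at the classifying test.* Rate = p/m, which does not depend on study end.
  - Test at month 2: 160/(200 × 2/12) = 4.80.
  - Test at month 4: 160/(200 × 4/12) = 2.40.
  - Test at month 6: 160/(200 × 6/12) = 1.60.

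The proportion is 160/200 = 80% in every row (Wilson 95% CI 73.9% to 85.0%). A rate under (a) or (c) matches p numerically only if mean person-time happens to be exactly one unit of time.

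**Two vaccine groups, followed for 6 and 9 months**

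| Assumed proportions | Ratio of proportions | Rates under (a) | Rates under (b), event at month 2 |
|---|---|---|---|
| Adequate, 80% v 80% | 1.00 | 1.60 v 1.07, ratio 1.50 | 3.43 v 2.82, ratio 1.21 |
| Non-response, 10% v 12% | 0.83 | 0.10/0.50 = 0.20 v 0.12/0.75 = 0.16, ratio 1.25 | 0.214 v 0.176, ratio 1.21 |

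The (b) figures in the second row, per 100 patients, are 10/(10 × 2/12 + 90 × 6/12) = 10/46.67 = 0.214 and 12/(12 × 2/12 + 88 × 9/12) = 12/68 = 0.176. Under both readings the group with less non-response shows the higher non-response rate. With equal follow-up under (a), the rate ratio equals the ratio of proportions and nothing is distorted.

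**The case against.** Five points can be made for the plan.

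- *Objective 1 itself mentions rates.* It does, but as an example in a parenthesis. The quantity to be described is frequency, and a loose use of *rates* for proportions would not justify a person-time denominator.
- *Time at risk ordinarily ends at the event, so counting responders to study end overstates the problem.* This stands in part. Reading (b) reduces the fall from 33% to 18%, and reading (c) removes the link to study end. A reader might infer that the rate must change with the study-end date. The documents do not support that without condition, because they do not say which reading applies.
- *Falling into a lower band on a repeat test does accrue over time.* This is true, so it would be too strong to say that a titer band can never be an event. But the plan defines no such event and no rule for repeat tests, and decline has its own objective (Objective 2). Waning also cannot explain an incidence rate for adequate response.
- *Crude frequencies may be derivable.* The table of characteristics by response level would probably show a count per level, and HIV status, as a listed covariate, may appear in it. It would be wrong to say that the frequency is lost or that HIV status is ignored. What is missing is any planned response proportion or interval, overall or by HIV status.
- *Proportions also depend on timing.* They do. Under an assumed decay (median 1,500 U/mL at day 21, natural-log SD 1.2, half-life 45 days), the share above 250 U/mL falls from 84% at day 60 to 44% at day 150. With a 90-day half-life it falls from 89% to 75%. The remedy has to deal with this.

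**Conclusion.** The plan is wrong as written on this point. The estimator named for a primary objective is not the quantity the objective asks for, and it omits the split by HIV status. That conclusion follows from the text and needs none of the assumed numbers.

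The size of the effect is conditional. In the assumed cohort, a three-month later study end lowers the adequate-response rate by 33% under reading (a), by 18% under (b) and not at all under (c), where test timing takes over. Misordering of vaccine groups arises under (a) and (b) when follow-up differs enough.

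A reader might infer that the vaccine comparison in this study will in fact be distorted. The documents do not support that: they give no timing by vaccine and plan no test between rates, so the size and direction of any distortion are unknown.

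**What to change.** In the synopsis and in Section 7 (Objective #1), replace the incidence-rate text with wording such as:

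> The proportion of patients with adequate, low and non-response will be estimated with 95% confidence intervals (for example Wilson) at the first eligible test after the primary series and before any booster, overall, by vaccine type and by HIV status.

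Because proportions also change with time since vaccination, show them by time band, or adjust for days since vaccination in any comparison of groups. Modified Poisson regression with robust variance and no person-time offset is one way to adjust. If descent into a lower band is of interest as an event, define it separately, with its own start and stop of risk.

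The cost is protocol wording and simpler programming. Vaccination, test and booster dates are already needed for eligibility and for Objectives 2 to 4. The downside is wider intervals within time bands, most of all for the least-used vaccine.
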